8.2. Secondary Objectives

 To retrospectively assess the efficacy consequences of NA and OIA, after adjusting for baseline characteristics and other confounders, overall and by cohort, on the odds of becoming unsuppressed, in subjects with and without resistance development. The protocol definition of unsuppressed is: HIV RNA>50 copies/mL in two consecutive measures within regimen duration, occurring within the observation period; among patient-regimens with HIV RNA ≤50 copies/mL at the start of the regimen if the regimen started during the observation period, or at the start of the observation period if the regimen started before the observation period.

In order to evaluate the odds of becoming unsuppressed (with or without resistance development), laboratory / monitoring data shall be collected.

• To retrospectively assess the effect of NA and OIA on the odds of hospitalization, after adjusting for baseline characteristics and other confounders, overall and by cohort.

In order to answer this objective, hospitalization data of all patient-regimens included in the study shall be collected.

To retrospectively assess the impact of NA and OIA on mean monthly ART plus hospitalization costs (Gross Domestic Product [GDP] Purchasing Power [PP] converted current prices), after adjusting for baseline characteristics and other confounders, overall and by cohort.

Ideally, hospitalization and ART costs will be collected at the center level. If not possible, hospitalization costs will be collected from publicly available national lists of diagnosis-related groups (DRGs) and ART costs from IMS databases of each participating country.

To assess the impact of STR versus non-STR on:

- 1. becoming unsuppressed (defined as above)
- 2. being hospitalized
- 3. costs (ART plus hospitalization costs)

To retrospectively quantify ART prescription errors during the first 48 hours of hospitalization of HIV-1 adult patients, overall and according to the cohort. Prescription errors will be evaluated by reviewing all prescriptions made during the first 48 hours of every hospitalization episode included. Investigators shall review all medication orders during this period to identify ART prescription errors. Errors will be classified as

- 1. Absence / incomplete regimen when the regimen prescribed is incomplete (e.g. when the physician prescribes only one PI/r) or when the regimen is not prescribed although it should have been.

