Odds of being hospitalized in STR versus non-STR groups, after adjusting for baseline characteristics and other confounders, using monitoring (hospitalization) data;

Odds of being hospitalized according to subject adherence level (NA and OIA), after adjusting for baseline characteristics and other confounders, using monitoring (hospitalization) data.

Costs

Average monthly ART plus hospitalization costs, adherence (OIA) adjusted, in each STR versus non-STR groups at GDP Purchasing Power Parity (PPP) converted current prices, after adjusting for baseline characteristics and other confounders;

Monthly ART plus hospitalization costs according to subject adherence level (NA and OIA), adherence (OIA) adjusted at GDP PPP converted current prices, after adjusting for baseline characteristics and other confounders.

Ideally, hospitalization and ART costs will be collected at the center level. If not possible, hospitalization costs will be collected from publicly available national lists of DRGs and ART costs from IMS databases of each country.

Prescription errors audit

Number of prescription errors in ART orders in the first 48 hours of hospitalization, overall and according to the cohort. Errors will be classified as:

- 1. absence / incomplete regimen
- 2. incorrect dosage
- 3. incorrect schedule
- 4. incorrect formulation
- 5. duplication of ART therapy
- 6. non-recommended drug-drug combinations (ART-ART and ART-non-ART), as suggested by Yehia et al {27744} and available on the HIV drug interaction website shown in red as contra-indicated; www.hiv-druginteractions.org/Interactions.aspx.

In order to collect this information, all prescriptions made during the first 48 hours of every hospitalization of all patient-regimens included shall be reviewed.

Taking into consideration the endpoints defined, the investigators believe that the study will answer the research questions.

Since this is a retrospective study that will only use data from subjects' clinical files and from prescription / laboratory and pharmacy files, treatment decisions will have already taken place, according to local treatment guidelines and/or routine clinical practice, and will not be influenced by the protocol.

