9.3. Subject Selection

Adherence study

For each included subject, data will be collected for all patient-regimens lasting for at least 90 days during the observation period, that either include Stribild or are EACS v7.0 recommended, once daily regimens containing two NRTI plus one NNRTI or two NRTI plus one PI/r. Two cohorts will be considered: (i) STR and (ii) non-STR (Figure 1).

Figure 1. Study Scheme of Adherence study.

Legend: \bigstar start of patient-regimen; \blacksquare end of patient-regimen; i) STR; ii) non-STR.

STR and non-STR subjects are defined, for administrative purposes, according to the type of regimen they were receiving on 31st December 2013. Note that these STR and non-STR groups of subjects are defined only for subject selection purposes. Once subjects are selected, the

relevant unit of analysis is a patient-regimen and both matching and the statistical analysis will be performed at the patient-regimen level.

A single subject may contribute to the analysis with 1 or more patient-regimens. Moreover, a subject selected as part of the STR group (because he was on STR on 31st December 2013) may contribute in the analysis for both the STR and the non-STR group as the example of subject Z or W, in Figure 1 above.

Data will be collected on patient-regimens that were ongoing between 1st January 2009 and 31st December 2013, this is the observation period, and subjects must have had at least one pharmacy refill in 2013. All patient-regimens must have started before 30th September 2013 to ensure a minimum duration of at least 90 days, as determined in the inclusion criteria. Although patient-regimens may have been started before the beginning of the observation period and may still be in progress at the end of this period, for the purposes of this study, generally only data from the observation period shall be collected. The data collection period is the time during which the centers will enroll eligible subjects and enter the data onto the eCRF.

The patient-regimen selection for the adherence study will involve the following steps, to be initiated as soon as hospital approval has been granted at each site:

- 1. Search in Pharmacy's electronic records the pharmacist will search the pharmacy electronic database in order to identify all patients who have at least one ART refill in 2013.
- 2. Separate these patients into two cohorts according to the regimen they were receiving on December 31st 2013 (STR cohort and non-STR cohort)

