Inpatient care (all episodes performed in the observation period)	 For each episode: Date of admission Admission diagnosis Date of discharge Destination at discharge Event code (DRG) ICD-9 or ICD-10 code (primary and secondary) Total cost of hospitalisation, including medications
Antiretroviral treatment pharmacy refills (for each valid patient-regimen)	 For each drug of each regimen: Date of refill (dd/mm/yyyy) scientific / generic name (which includes active principles, dosages, pharmaceutical forms), Quantity dispensed
Adverse Drug Reactions	 For each episode Adverse Drug Reaction description Seriousness Start and End dates or ongoing Relation to Gilead drug
Pregnancy (if applicable)	 Last menstrual period Date of pregnancy confirmation Estimated date of delivery or outcome if available at the time of the review

Prescription errors sub-study

After confirmation of eligibility criteria, investigators will collect the following data for each hospitalization episode selected, based on clinical/pharmacy/prescription records:

Individual characteristics (at the beginning of each hospitalization enigode)	- Subject initials (where permissible)
	- Date of birth
episode)	- Gender (male, female, transgender)
	- Race (White, Asian, Black or African heritage, other)
	- Non ART concomitant medications
Inpatient care (for each hospitalization	- Date of admission
episode)	- Admission diagnosis
	- Date of discharge
	- Discharge diagnosis
	- Destination at discharge
	- ICD-9 or ICD-10 code (primary and secondary)
	- DRG code Admitting service: HIV/AIDS, Medicine, Surgery, Obstetrics and Gynaecology, Neurology / Psychiatry, Other
	- Degree of the prescribing physician: Assistant / Junior doctor, Graduated Assistant / Registrar, Senior Graduated Assistant / Consultant, Other
	- Transferred within the first 48 hours? If so where to and when?
	- ART prescribed in the first 48 hours: active substances, dosage of each, scheduling
Prescription errors audit (for each error)	- Type of error:
Prescription errors audit (for each error)	 Type of error: (1) absence / incomplete regimen
Prescription errors audit (for each error)	 Type of error: (1) absence / incomplete regimen (2) incorrect dosage [including renal dose adjustment]
Prescription errors audit (for each error)	 Type of error: (1) absence / incomplete regimen (2) incorrect dosage [including renal dose adjustment] (3) incorrect schedule

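### The cost endpoints are set at current prices over 2009-2013 with no common price year, so a price trend shared by both cohorts can enter the STR cost contrast if STR regimens lie later in the window

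*Protocol*

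**What the plan says.** All references are to the Protocol.

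- **Price basis.** The cost objective in section 8.2 is set at "Gross Domestic Product [GDP] Purchasing Power [PP] converted current prices". In section 9.1, the STR versus non-STR cost endpoint is "Average monthly ART plus hospitalization costs, adherence (OIA) adjusted, in each STR versus non-STR groups at GDP Purchasing Power Parity (PPP) converted current prices". The endpoint by adherence level is "adherence (OIA) adjusted at GDP PPP converted current prices, after adjusting for baseline characteristics and other confounders". None of these places names a price year, an index or a deflator.
- **Time span.** Section 9.3: "Data will be collected on patient-regimens that were ongoing between 1st January 2009 and 31st December 2013, this is the observation period".
- **Admission costs.** Table 2 in section 9.4 collects, for each inpatient episode, "Total cost of hospitalisation, including medications".
- **ART costs.** The same table collects refill date, product and quantity dispensed, but no price per refill.
- **Source of prices.** Sections 8.2 and 9.1 prefer costs from the center. Failing that, "hospitalization costs will be collected from publicly available national lists of DRGs and ART costs from IMS databases of each country". The year of those lists is not given.
- **Analysis.** Section 9.8 names a linear mixed model as suitable for cost and says that the panel structure will be accounted for. The synopsis treats all collected variables as potential confounders.

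**The concern.** A cost averaged over five calendar years needs one unit of money. Taken in its usual sense, the stated price basis leaves a 2009 admission in 2009 money and a 2013 admission in 2013 money. Parity conversion makes Italy, Portugal, Spain and the UK comparable, but it does not put 2009 and 2013 on one price level.

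This affects the comparison only if the cohorts sit at different points in the window. In that case general inflation, tariff revisions or list-price changes that apply equally to STR and non-STR would be read partly as a cost effect of STR. Economic benefit of STRs is one of the study's stated hypotheses (section 8), so the contrast should not carry a component that has nothing to do with the regimen.

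**Working it through.** The protocol gives no cost figure, price trend or calendar mix, so there is no stated number to reproduce. The check asks whether the design allows a calendar gap and how large the effect would be under open assumptions.

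**Step 1: which costs are in the money of their own year?** Admission totals are recorded per episode, so on the ordinary reading they are nominal. ART has quantities only and must be valued with unit prices from the center or from IMS data, of an unstated year. If ART is valued from a single list and admissions are nominal, only the admission share of monthly cost drifts. Centers reporting their own costs and centers using national lists could also be on different price bases within one average.

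**Step 2: can the cohorts differ in calendar time?** Section 9.3 assigns subjects for selection by the regimen in use on 31 December 2013, then analyzes all their valid regimens. A subject selected as STR may contribute non-STR regimens, and these necessarily precede the regimen in use on the last day. The converse holds for subjects selected as non-STR. The net gap therefore depends on which direction of switching dominates. Section 9.6 cites, for sizing, a study of patients moving from non-STR to STR. If that direction dominates, STR regimens lie later. The protocol does not quantify this.

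**Step 3: closed form.** Let g be the annual price change common to both cohorts and D the gap in mean calendar time (STR minus non-STR, in years). Both are assumptions. With equal true cost,

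spurious relative difference = (1 + g)^D - 1.

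At D = 0.55 years, from an assumed 80%/20% split of switch direction:

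| g per year | calculation | spurious STR difference |
|---|---|---|
| +1% | 1.01^0.55 - 1 | +0.5% |
| +3% | 1.03^0.55 - 1 | +1.6% |
| +5% | 1.05^0.55 - 1 | +2.7% |
| -5% | 0.95^0.55 - 1 | -2.8% |

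At D = 0 the result is 0% for any g. At D = 1 and g = +3% it is +3.0%; at D = 2 and g = +3% it is +6.1%.

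**Step 4: simulated range of D.** This used 700 STR and 805 non-STR subjects and an average of 1.5 regimens each (sections 9.3 and 9.6). Assumptions: half the subjects have two regimens, the switch time is uniform between 0.25 and 4.75 years, subjects selected as non-STR have only non-STR regimens, there is no true cost difference, and all cost is at nominal prices. There was no matching or covariate adjustment.

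| Earlier regimens of switching STR subjects that were non-STR | mean gap (years) | g = +3% | g = +5% | g = -3% | g = -5% |
|---|---|---|---|---|---|
| none | 0 | about 0% | about 0% | about 0% | about 0% |
| half | 0.41 | +1.2% | +2.0% | -1.3% | -2.1% |
| all | 0.91 | +2.7% | +4.4% | -2.8% | -4.7% |

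The 0.55-year gap of Step 3 lies within this range.

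**Step 5: after the change.** With every cost at one price year, the multiplier is the same for all regimens, and the spurious difference from a common price trend is 0% for any g and D.

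**The case against.** The strongest reply is that the term is ambiguous. It may mean one price list in force at the time of analysis, and then nothing drifts. This is most plausible under the DRG and IMS fallback, and for ART, which has no recorded price per refill. The text does not settle it. But recorded totals of 2009-2013 admissions are not at one recent price list, so that reading also needs a statement of the year and a rule for admissions.

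It can also be said that costing detail belongs in a statistical analysis plan, which is not at hand. That would answer a complaint about silence. Here the protocol states a price basis, in section 8.2 and twice in section 9.1, and the point concerns that statement.

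Four stronger readings are tempting, and the documents do not support them:

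- **That the bias is certain.** It needs a calendar gap, which the design permits but does not establish.
- **That the cost model has no time term.** Section 9.8 does not fix the covariates. The synopsis makes all collected variables, dates included, potential confounders; section 9.3 selects propensity covariates by association with STR; and section 9.8 promises to respect the panel structure. Regimen calendar time is not named, but neither is it excluded.
- **That cost by adherence level is distorted in the same way.** This would require adherence to vary by calendar year, and nothing in the protocol says that it does.
- **That the effect is as large as the price change across the whole window.** At 3% per year, identical care in 2009 and 2013 differs by 1.03^4 - 1 = 12.6%, but that is not the study contrast, which depends on the gap in mean calendar time. A false-positive rate would also need the variability of monthly cost, which the protocol does not give.

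**Conclusion.** The point holds in a conditional form. The protocol values its secondary cost endpoints at current prices across five years and names no common price year. On the ordinary meaning, money of different years is pooled, and parity conversion does not correct this. A price trend common to both cohorts can then enter the STR cost contrast if STR regimens lie later in the window.

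The size is modest and rests on assumptions: about 1.6% at 3% per year, and 2.7% to 2.8% in size at plus or minus 5% per year, for an assumed gap of 0.55 years. It is zero without a gap. It is smaller if ART is valued from one list, and smaller again if the fitted model or the matching accounts for regimen calendar time. The sign follows the trend: with STR later, rising prices make STR look dearer and falling prices make it look cheaper. The primary adherence endpoint is not touched.

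**What to change.** In sections 8.2 and 9.1, replace current prices with constant prices of one stated reference year, for example 2013, and add the rule:

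- value all ART dispensed at that year's unit prices for the country or center;
- bring every admission cost to that year, either with a national price index or by applying that year's DRG tariff to all episodes;
- convert with that year's GDP purchasing power parity.

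If a single recent price list was intended from the start, say so, name its year and apply it to admissions as well as ART.

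Naming regimen calendar time as a covariate would be a lighter step and would help the contrast, but the reported average monthly costs would still be in money of mixed years.

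The cost is a change of wording, the unit prices of the chosen year and one price-index table for each of the four countries. Refill and admission dates are already collected. The small downside is that the result is no longer the nominal amount paid, which can be shown as a descriptive line.

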9.2. Population

The population being studied are HIV-1 infected adult patients on ART, recruited from centers in Italy, Portugal, Spain and UK by Investigators that have expertise in the management of HIV infection.

Adherence study

HIV-1 infected adults who received ART between 1st January 2009 and 31st December 2013 for at least 90 days.

Inclusion criteria:

- HIV-1 infected
- Aged 18 or above at the beginning of the observation period
- Able and willing to provide informed consent
- At least one pharmacy refill in 2013
- Being followed at the center at the time of recruitment
- Has been on an ART regimen recommended by EACS v 7.0 {27774}, which contains two NRTI plus one NNRTI or two NRTI plus one PI/r, or Stribild, and which was taken once daily for at least 90 days on 31st December 2013.
- Availability of a complete electronic history of pharmacy refills throughout the observation period.

Exclusion criteria:

- Subject participation in an interventional study during the observation period
- Subject on a non-pill formulation during the observation period
- Subject on off-ART periods (ART holidays) during the observation period.

Prescription errors sub-study:

Subjects enrolled in the sub-study do not need to be participating in the adherence study in order to be eligible.

Inclusion criteria:

- HIV-1 infected patients who were hospitalized, at least for a minimum of 48 hours between 1st January 2012 and 29th December 2013 and who received, or should have received, an ART regimen during the first 48 hours of the hospitalization episode;
- Aged 18 or above at the beginning of the hospitalization episode;
- Able and willing to provide informed consent
- Availability of complete history of medication (ART and non-ART) prescribed during the first 48 hours of the hospitalization episode.

Exclusion criteria:

• Subject participation in an interventional study during the observation period

9.3. Subject Selection

Adherence study

For each included subject, data will be collected for all patient-regimens lasting for at least 90 days during the observation period, that either include Stribild or are EACS v7.0 recommended, once daily regimens containing two NRTI plus one NNRTI or two NRTI plus one PI/r. Two cohorts will be considered: (i) STR and (ii) non-STR (Figure 1).

Figure 1. Study Scheme of Adherence study.

Legend: \bigstar start of patient-regimen; \blacksquare end of patient-regimen; i) STR; ii) non-STR.

STR and non-STR subjects are defined, for administrative purposes, according to the type of regimen they were receiving on 31st December 2013. Note that these STR and non-STR groups of subjects are defined only for subject selection purposes. Once subjects are selected, the

relevant unit of analysis is a patient-regimen and both matching and the statistical analysis will be performed at the patient-regimen level.

A single subject may contribute to the analysis with 1 or more patient-regimens. Moreover, a subject selected as part of the STR group (because he was on STR on 31st December 2013) may contribute in the analysis for both the STR and the non-STR group as the example of subject Z or W, in Figure 1 above.

Data will be collected on patient-regimens that were ongoing between 1st January 2009 and 31st December 2013, this is the observation period, and subjects must have had at least one pharmacy refill in 2013. All patient-regimens must have started before 30th September 2013 to ensure a minimum duration of at least 90 days, as determined in the inclusion criteria. Although patient-regimens may have been started before the beginning of the observation period and may still be in progress at the end of this period, for the purposes of this study, generally only data from the observation period shall be collected. The data collection period is the time during which the centers will enroll eligible subjects and enter the data onto the eCRF.

The patient-regimen selection for the adherence study will involve the following steps, to be initiated as soon as hospital approval has been granted at each site:

- 1. Search in Pharmacy's electronic records the pharmacist will search the pharmacy electronic database in order to identify all patients who have at least one ART refill in 2013.
- 2. Separate these patients into two cohorts according to the regimen they were receiving on December 31st 2013 (STR cohort and non-STR cohort)
- 3. Perform center level random sampling It is likely that the number of subjects identified above is higher than the number of subjects agreed in the present protocol (average of 80 subjects in the STR and 90 subjects in the non-STR cohort, per center). In such case, each investigational center will select a sample of subjects from their population, instead of including the entire population. Therefore, a sampling mechanism will be used. Participating subjects will be randomly selected from the list of subjects and stratification by cohort will be considered (stratified random sampling). In stratified random sampling, separate random samples will be selected from the two cohorts created (STR and non-STR). Each center will prepare two separate lists with subjects' unique identifiers (subject hospital number) for each cohort. The random samples will be obtained using Microsoft Excel®:
 - The list of subjects' unique identifiers will be put in a column of an empty sheet;
 - A second column will be created to the left (it must be to the left) of the subjects' identifiers by writing "=RAND()" in each cell and random numbers from 0 to 1 will appear;
 - The column with the random numbers will be copied and pasted as values in the same cells, so the random numbers won't change;

- Finally, the "Sort" button from the "Sort and Filter" group in the "Data" ribbon will be clicked (both "smallest to largest" or "largest to smallest" sorting may be used) and a randomly sorted list of subjects' identifiers will be obtained;
- Repeat the procedure for the other cohort.

In the STR cohort, priority will be given to non-Atripla subjects. As such, if a center has more than the number of pairs to be included, e.g. 80 subjects on Eviplera or Stribild, the methodology described above applies directly to the population of subjects on Eviplera or Stribild. If a center does not have any other STR except for Atripla, the methodology described above applies directly to the population of subjects on Atripla. If a center has less than 80 subjects on Eviplera or Stribild then these are included and the remaining will be selected using the methodology described above, from the population of Atripla subjects.

The non-STR cohort will be oversampled to a 1:1.15 ratio, so 90 subjects need to be selected.

The subjects to be selected are the first ones from each sorted list of the random numbers. For example, if 80 subjects are to be selected in the STR cohort, the top 80 in the list are to be included.

For the selected subjects, check Inclusion and Exclusion criteria. If one subject does not meet the criteria, replace that subject with the next on the list (subject 81 in the example above). Repeat as necessary replacing each subject which does not meet the criteria by the next in the list. The same procedure should be followed if a subject meets the criteria but does not sign the informed consent.

Note that subjects are being selected instead of patient-regimens, so it is not obvious how many patient-regimens will be included. Nonetheless, considering that an average of 1.5 regimens in a 5 year period is likely to occur, then the 700 STR subjects and the 805 non-STR subjects will yield more than enough patient-regimens to reach the required patient-regimen sample size.

A Propensity Score Matching (PSM) approach will be applied subsequently on the merged dataset from all sites in order to maximize homogeneity between cohorts and reduce the impact of treatment-selection bias. A variable ratio between cohorts will be considered, so that 700 STR subjects are selected as cases and 805 non-STR as controls. The propensity score is defined as a subject's probability of receiving a specific treatment (STR) conditional on the observed covariates {27771}. When propensity scores are used in matching, treatment effects are unbiased when treatment assignment is strongly ignorable {27756}. On the other hand, treatment assignment is strongly ignorable if treatment cohorts and the outcome variable are conditionally independent given the covariates. This independence assumption will not hold in situations where there are variables not included as propensity score covariates that are correlated with outcome events and time dependent treatment selection {27757}.

The PSM procedure will include 4 steps:

- 1. Model choice: The propensity score will be computed using binary regression with a logit or a probit link function, depending on model fitting statistics. Statistical based criteria will be used to specify the covariates, such as the degree of association with STR odds.
- 2. Matching algorithm choice: The nearest neighbor algorithm or the nearest neighbor within a specified caliper distance algorithm will be used as a matching algorithm. The nearest neighbor matching selects for matching to a given STR subject the non-STR subject whose propensity score is closest to that of the STR subject. Nearest neighbor matching within a specified caliper distance is similar to nearest neighbor matching with the further restriction that the absolute difference in the propensity scores of matched subjects must be below some pre-specified threshold (the caliper distance) {27758} {27759}. The choice between one of these approaches will rely on how much data will be collected.
- 3. Sample balance diagnosis: Sample balance will be checked using the methods proposed by Ho et al. including standardized means, comparing higher-order moments, propensity-score summary statistics or empirical quantile-quantile plots for each variable {27772}.
- 4. Matching: Assign the matching membership and retain the propensity score for the case where further adjustment is needed.

Prescription errors sub-study

In this sub-study, unit of analysis will be a hospitalization episode of HIV-1 infected adult (due to any reason) in which there was a prescription of ART during the first 48 hours. Two cohorts will be considered: (i) STR and (ii) non-STR. Subjects will be enrolled that were hospitalised between 1st January 2012 and 29th December 2013.

For the prescription errors sub-study, subject selection will involve the following steps, to be initiated as soon as hospital approval has been granted at each site:

- 1. Search in the hospital registry to identify all hospitalization episodes of HIV-1 infected patients with admission date 1st January 2012 and 29th December 2013.
- 2. Check Inclusion criteria once identified, the Investigator will check whether those hospitalization episodes meet the inclusion criteria.
- 3. Perform center level random sampling It is likely that the number of eligible episodes identified above is higher than the number of episodes the center is willing to include. In such case, each investigational center will select a sample of 40 episodes from their population, instead of including the entire population. Therefore, a sampling mechanism will be used. Episodes to be included will be randomly selected from the list of eligible episodes and stratification by cohort will be considered (stratified random sampling). In stratified random sampling, separate random samples will be selected from the two

cohorts created (STR and non-STR). Two separate lists with episodes' unique identifiers for each cohort will be prepared. The random samples will be obtained using Microsoft Excel®:

- The list of episodes' unique identifiers will be put in a column of an empty sheet;
- A second column will be created to the left (it must be to the left) of the patient-regimens' identifiers by writing "=RAND()" in each cell and random numbers from 0 to 1 will appear;
- The column with the random numbers will be copied and pasted as values in the same cells, so the random numbers won't change;
- Finally, the "Sort" button from the "Sort and Filter" group in the "Data" ribbon will be clicked (both "smallest to largest" or "largest to smallest" sorting may be used) and a randomly sorted list of episodes' identifiers will be obtained;
- Repeat the procedure for the other cohort.

The episodes to be selected are the first ones from each sorted list. As a guidance rule, even samples of episodes from each cohort should be obtained. Information of eligible hospitalization episodes shall be recorded on the eCRF.

